Study Purpose	The purpose of the study is to collect safety and efficacy data on the performance of the study stoma site accessory when used to prevent abdominal wall leakage for patients with a long term feeding tube. This accessory has been developed by the Cleveland Clinic and will be used for the first time in human subjects according to the labeled indication for clinical use in accordance with the Manufacturer's Instructions for Use based on other similar, FDA approved gastrostomy and jejunostomy enteral feeding tube accessory components. After providing informed consent, eligible patients will receive a study stoma site accessory during a feeding tube replacement procedure the patient is scheduled to have as a standard of care procedure.
Study Design	Single site, prospective, phase I, non-randomized safety and efficacy of feeding tube stoma site accessory for patients with enteral feeding tubes.
Primary Endpoints	Safety and efficacy of the study stoma site accessory as evidenced by successful study accessory placement at time of initial replacement procedure, post procedure adverse events including recurrence of any documented preprocedure [abdominal surface] condition and repeat intervention up to 6 months after the initial replacement procedure.
Secondary Endpoints	Patient Quality of Life is hypothesized to improve significantly with leak reduction, therefore various Quality of Life questionnaires will be collected at baseline, 2 weeks and 6 months or early termination.
Patient Population	 Inclusion Criteria: Male or female, aged ≥22 and ≤85. Note: Because the study accessory is designed for adult use, participants <22 years of age are excluded but will be eligible for future trials, if applicable. Ability to understand and the willingness to sign a written informed consent document.

	-

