Study Monitoring	Site monitoring will be performed internally by Cleveland Clinic Clinical Research Personnel.

Purpose

The purpose of the study is to collect safety and efficacy data on the performance of the study stoma site accessory when used to prevent abdominal wall leakage for patients with a long term, ≥ 3 months, enteral feeding tube including, gastrostomy or jejunostomy tubes. This study accessory has been developed by the Cleveland Clinic (CC) for clinical use in human subjects and will be used according to the labeled indication and in accordance with the Manufacturer's Instructions for Use based on other similar, Food and Drug Administration (FDA) approved enteral tube stoma site accessory components. Patients receiving the study accessory will also be asked pre-procedure and post-procedure quality of life questions to identify change in quality of life. After providing informed consent, eligible patients will receive a study stoma site accessory during an upcoming enteral tube replacement procedure the patient is scheduled to have as a standard of care procedure.

Background

Nutrition therapy where liquid formula or food is delivered to the gastrointestinal tract to supplement or provide all caloric intake by a tube for patients with a functional GI tract is known as enteral nutrition (EN). Since the first use of endoscopic gastrostomy tube for EN was documented in late 1970 by Gauderer et al.[1] use of several additional types of feeding tubes have been widely reported. Tubes, such as, percutaneous endoscopic gastrostomy (PEG,) PEG with jejunal extension (PEGJ) and direct percutaneous endoscopic jejunostomy (DPEJ) have been reported to offer long term solutions for nutrient and medication delivery to patients with intact and functional GI tracts [2] who have a variety of underlying diseases. Design modifications allowing the placement procedure to be technically easier and safer have been made over the years but very few modifications have been made to the kit component parts throughout this same period of time. [2]

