 - o Curvature and ribs to prevent accessory component from migrating
 - Indented to retention bumper
- Retention accessory bumper
 - Cupped, to allow greater mobility of flexible tubing
- Introducer
 - A double tapered plastic rod to assist the stoma site accessory plug onto the feeding tube. One end will insert into the distal end of the feeding tube. The accessory plug will be put onto the opposite end of the introducer and slide toward feeding tube.

Duration of implant or exposure

The average life span of PEG tubes is reported to be three months with tube degradation being the primary reason for replacement.[5] The study stoma site accessory is anticipated to be compatible with this duration based on similar SOC flange and button accessories. Maximum duration is unknown but could be significantly longer. Many commercial insurers will cover up to four tube replacements per calendar or rolling year. For study purposes the maximum length of time during which data will be collected for tubing change, as ordered by the treating physician, will be 6 months from initial study accessory placement.

[figure not shown]

Fig7. The study stoma site accessory depicting prevention of stomach acid from leaking on the abdominal wall.

Labeling/Accessory Tracking

The study stoma site accessory components will be sterilized by Cleveland Clinic's OR Surgical Processing Department. One retention bumper and one introducer will share one package since they are identical respectively in size. The accessory plug component will be in a separate package, labeled by size compatibility, e.g., "16 Fr, 20 Fr". All components will be double wrapped, barcoded and assembled as kits. Kits will be delivered for accountability and storage at room temperature in the Internal Medicine Research Unit (IMRU) located on the Cleveland Clinic (CC) Main Campus study site. Kits will be secured in a locked cabinet, accessible only to study personnel. Study personnel will maintain and monitor usage on a Case Report Form. IMRU study personnel can readily provide the study stoma site accessory kits to any procedure area on the Main Campus at short notice.

Manufacturing Information

Dow Corning® QP1-250

Dow Corning Corporation

Technical Data

Product Description

Liquid Silicone Rubber materials for device and component fabrication in the healthcare industry

APPLICATIONS

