6 month (180 \pm 7 days; 173-187 days after the index procedure)
```

The follow-up visit at 2 weeks can be scheduled as in-person or a virtual visit and will include:

- General Assessment of the abdomen with stoma site inspection
- Characteristics of pain and leakage questionnaire
- Abdominal Pictures
- Medications of Interest
- Oral Temperature Log Review
- Oral Temperature
- Adverse events

The follow-up phone calls at weeks 4, 6 and after an unscheduled visit will include the following:

- Characteristics of pain and leakage questionnaire
- Medications of Interest
- Adverse events

The follow-up visit at months 3 and 4 will be virtual or in-person and include:

- General Assessment of the abdomen with stoma site inspection
- Characteristics of pain and leakage questionnaire
- Abdominal Pictures
- Medications of Interest
- Oral Temperature
- Adverse events

The follow-up visit at month 6 will be in-person and include:

- General Assessment of the abdomen with stoma site inspection
- Feeding tube change with removal of study device and replacement with SOC tubing
- PROMIS 10
- Tobacco use questionnaire
- Characteristics of pain and leakage questionnaire
- Medications of interest
- Adverse events

If early termination occurs, study personnel will attempt to collect the following:

- General Assessment of the Abdomen with stoma site inspection
- PROMIS 10
- Tobacco use questionnaire
- Characteristics of pain and leakage questionnaire
- Medications of Interest
- Vitals

Any unscheduled visits discovered during follow-up phone calls or patient reported will be recorded on the appropriate case report form (CRF); The reason for the visit, adverse events of interest, treatments, interventions, hospitalizations and those resulting in early termination will be captured.

A Study Completion CRF should be completed at Month 6. The Investigator also must provide follow-up medical care for all patients who are prematurely withdrawn from the study, or must refer them for appropriate ongoing care.

SCREEN FAILURES

Participants who are consented to participate in the clinical trial, who are scheduled for enteral feeding tube replacement with the study stoma site accessory and who are determined by the attending clinician investigator at the time of intervention to be inappropriate candidates for anatomical or medical reason, e.g., requiring sedation, not previously ascertained during the screening procedures, are considered screen failures.

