accessory as evidenced by rate of	defined as placement of the device at	accessory viability; its			
successful device placement and	the intended location, including securing	safety and efficacy for			
related post procedure adverse	of the device in place and its	use in a general			
events.	effectiveness at the week two [2] exam.	population of patients			

OBJECTIVES	ENDPOINTS	JUSTIFICATION FOR ENDPOINTS
The study will focus on the known minor risks of tube leakage associated with feeding tube components including recurrence of any documented pre-procedure [abdominal surface] condition, new condition or repeat intervention up to 6 months after the initial replacement procedure.	Patients will be followed up to 6 months after the index procedure. However, any patient who requires re-intervention that compromises the study stoma site accessory integrity (e.g., study accessory is removed and replaced with standard of care components or otherwise damaged) subsequent to the initial replacement procedure will no longer be followed but will be included in the analysis of the endpoints until the time of re-intervention. Rate of post-procedure adverse events to be collected from initial replacement procedure through month 6, including but not limited to: Dermatitis Cellulitis Accessory migration over 1 cm An adverse event determined as related or possibly related Allergic reaction to the accessory material	displaying a broad range of disease processes for which they will be receiving EN or HEN for ≥ 3 months.
Secondary		
Change in patient quality of life after intervention as self-reported by participants. Outcomes will be collected at various intervals.	Various participant reported outcomes will be collected at baseline, week 2 and month 6: PROMIS 10, nationally validated quality of life survey tool Alcohol/ tobacco use Study accessory management questions Characteristics of pain and leakage at site of study accessory placement	Demonstrated ability to predict clinical benefit to patients with enteral feeding tubes.

Table 3

Hypothesis Testing

This is not a hypothesis driven study. The study is a pilot trial to determine safety and efficacy of a feeding tube accessory and feasibility of determining improvement of patient quality of life using pre and post measures. Patient quality of life assessment will be collected at baseline and 6 months for comparison.

Data Collection and Analysis

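### Table 3 assigns four of the six scheduled post-placement leakage readings to no endpoint, so a leak between week 2 and month 6 counts only through adverse-event recording or re-intervention

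*Combined protocol and SAP*

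**What the plan says.** The Purpose section describes the accessory "when used to prevent abdominal wall leakage for patients with a long term" feeding tube in place, defined as at least 3 months.

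Table 3 (Primary Outcome Measures) gives the primary objective two parts. The first is a procedural-success rate: placement at the intended location, securing of the device, and its "effectiveness at the week two [2] exam". The second runs to six months. Its objective reads "The study will focus on the known minor risks of tube leakage associated with feeding tube components including recurrence of any documented pre-procedure" abdominal-surface conditions, and it goes on to new conditions and repeat intervention. Its endpoint is "Rate of post-procedure adverse events to be collected from initial replacement procedure through month 6, including but not limited to" dermatitis, cellulitis, migration over 1 cm, related or possibly related events, and allergic reaction. Leakage is not among the items named.

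The secondary row of Table 3 says "Various participant reported outcomes will be collected at baseline, week 2 and month 6", and characteristics of pain and leakage are among those outcomes. The Synopsis adds early termination to these times.

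The data collection is wider. Table 1 marks the pain and leakage questionnaire at every post-placement contact. The Follow-Up section agrees: "The follow-up phone calls at weeks 4, 6 and after an unscheduled visit will include the following", and the list that follows includes that questionnaire. The month 3 and month 4 visits include it too.

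**The concern.** The outcome the device targets is measured repeatedly over six months, but the endpoint definitions use only the first and last of those measurements. The effectiveness part of procedural success is fixed about 14 days after a new tube is placed.

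Consider a patient who is dry at week 2, reports leakage by telephone at week 6 and again at month 3 without skin damage or a tube change, and is dry at month 6. This patient is a procedural success, and both named post-placement leakage readings are clean. Whether the leak appears anywhere in the results depends on whether someone records it as an adverse event.

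The study is descriptive and has ten patients, so its result is whatever the endpoint definitions count. If leaks between week 2 and month 6 are counted inconsistently, the report could present week-2 effectiveness as evidence of leak prevention with a long-term tube when the collected data show otherwise.

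**Working it through.** The plan states no leakage rate, power or effect size, so there is no figure to reproduce. The check sets the collection schedule against the endpoint definitions.

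| Post-placement reading | Leakage questionnaire collected (Table 1, Follow-Up) | Named in an endpoint |
|---|---|---|
| Week 2 | yes | yes: effectiveness and secondary row of Table 3 |
| Week 4 | yes | no |
| Week 6 | yes | no |
| Month 3 | yes | no |
| Month 4 | yes | no |
| Month 6 | yes | yes: secondary row of Table 3 |
| After an unscheduled visit | yes | no |
| Early termination | yes | not in Table 3; yes in the Synopsis secondary endpoint, and Table 1 footnote 2 collects it for reporting |

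Scheduled readings: 6. Named in Table 3: 2. Unassigned: 6 − 2 = 4.

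Follow-up after the effectiveness reading, using the nominal days in the Follow-Up section: 180 − 14 = 166 days, and 166/180 = 92%.

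Data Collection and Analysis specifies frequencies, percentages and 95% confidence intervals. It has no rule for combining repeated leakage readings.

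**Illustration of size.** The documents give no per-visit leak rate, so assume a probability q of a leak at each reading, independent across readings. The share of patients who leak only at the four unassigned readings is (1 − q)² × [1 − (1 − q)⁴]. The chance of at least one such patient among ten is 1 − (1 − share)¹⁰.

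| q (assumed) | Dry at week 2 | Dry at week 2 and month 6 | Dry at all six | Leak only at the unassigned four | At least one such patient in ten |
|---|---|---|---|---|---|
| 0.05 | 95% | 90% | 74% | 17% | 84% |
| 0.10 | 90% | 81% | 53% | 28% | 96% |
| 0.20 | 80% | 64% | 26% | 38% | 99% |

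For a given q, leaks that cluster within patients would generally lower the last two columns. Some of these patients would also reach the adverse-event endpoint, so the columns show who falls outside the named leakage readings, not who is lost altogether.

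A count example, also assumed: 10/10 dry at week 2 is 100% (exact 95% CI 69.2% to 100%). If four of those ten leak by month 4, the leak-free share is 6/10 = 60% (26.2% to 87.8%).

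**The case against.** The strongest reply is that later leaks are already covered. Table 3's second primary part concerns tube-leakage risks up to six months, and its adverse-event list is open. The Known Potential Risks section puts tube leakage first among the minor risks. The adverse-event section collects mechanical events throughout the study, and adverse events are asked about at weeks 4 and 6 and months 3 and 4. The Synopsis counts "repeat intervention up to 6 months after the initial replacement procedure" in the primary endpoint. A week-2 reading is also normal for procedural success in a ten-patient pilot.

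Much of this stands, and it rules out four stronger readings that a reader might infer:

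- That a leak between week 2 and month 6 never counts against the accessory. It can enter the primary adverse-event rate or count as re-intervention.
- That week-2 effectiveness is the only efficacy evidence in the primary endpoint. The Synopsis and Table 3 rest safety and efficacy jointly on placement and on events to month 6.
- That a patient who leaks and exits for a tube change disappears as a silent success. Procedural success is unchanged, but the re-intervention counts, data to that point are analysed, and an early-termination leakage questionnaire is sought.
- That leakage is most likely to return near three months. The protocol does say "The average life span of PEG tubes is reported to be three months with tube degradation being the primary reason for replacement", but that concerns degradation. Known Potential Risks describes leakage as frequent in the first days after placement and possible at any time in a mature tract.

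The reply does not show that later leaks will be counted. An open list permits leakage to be recorded without requiring it. Re-intervention is not specific to leakage, since degradation is given as the main reason for tube replacement. A pooled adverse-event rate also cannot give the proportion of patients who stayed dry.

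**Conclusion.** The point holds in a limited form. Four of six scheduled post-placement readings of the target outcome, and those after unscheduled visits, belong to no named endpoint. A leak at those times cannot alter the procedural-success rate. It counts only through adverse-event recording, a recurrent or new abdominal-surface condition, or repeat intervention, so one with none of these consequences can go uncounted.

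The counts (4 of 6 readings, 166 of 180 days) come directly from the documents. The percentages by q and the 100% versus 60% contrast rest on assumed leak rates and show only possible size. The contrast further assumes that effectiveness means absence of leakage. Table 3 does not define the term, which is a separate gap.

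This does not invalidate the design, but it should be settled before the data are analysed.

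**What to change.** - Keep week 2 as the procedural-success reading, and describe any effectiveness conclusion drawn from it as short-term.
- Add to Table 3 a descriptive leakage endpoint through month 6 or accessory removal, using every scheduled, unscheduled and early-termination questionnaire already collected. Report:
  - (a) the proportion with leakage at each of weeks 2, 4 and 6 and months 3, 4 and 6, showing the number with the accessory still in place and the number who have exited, with reasons;
  - (b) the proportion of all patients with successful placement who have any reported leak from week 2 to removal, counting a leak at early termination as a leak and keeping exited patients in the denominator, with an exact 95% confidence interval. Show beside it how many exited without a recorded leak. Because patients withdrawn before week 2 are replaced, this denominator may exceed ten.
- Align Table 3 with the Synopsis and Table 1 footnote 2 on early termination.
- State when a leak reported on the questionnaire is recorded as an adverse event.

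The cost is revised Table 3 wording, a recording rule and one extra summary table, with no new visits or data. The efficacy figure may be less favourable.

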	 Patients with existing gastrostomy and jejunostomy enteral feeding tubes, placed ≥ 3 months, undergoing replacement of feeding tube inpatient or outpatient. Willing to adhere to placement of study stoma site accessory and ability to take oral temperature at specified times. Stated willingness to comply with all study procedures and availability for the duration of the study. Willing to adhere to removal of study stoma site accessory at mo. 6 Exclusion Criteria Patient requires general anesthesia in an OR for tube changes Current use of steroids (any dose) daily ≥ 3 months including, but not limited to: prednisone, prednisolone, methylprednisolone, cyclosporine Current use of Immunosuppressants including, but not limited to: azathioprine, mycophenolate. BMI ≥ 40 Non-English speaking patients. Pregnant Women. Known allergic reactions to components of the study stoma site accessory: Medical Grade Silicone as described in Technical Data Prospectus from Dow Corning Corporation. Treatment with another investigational drug or device within 6 months of screening/baseline. Uncontrolled illness, recent open abdominal surgery or social situations that in the opinion of the investigative team would limit compliance with study requirements, including, but not limited to: Ongoing or active infection Psychiatric illness Unable to self-report Not ambulatory and incapable of carrying out all self-care Unsuccessful study accessory placement at initial replacement procedure
Number of	The study will enroll until 10 patients have had successful study stoma
	site accessory placement and reached the 2 week research follow-up
Subjects	visit.
Number of Sites	1
Sample Size	The sample size is 10 subjects. No formal sample size calculations were
Justification	performed for pre-market safety and efficacy data.
Study Hypothesis	The study is a pilot trial to access feasibility and safety with the aim to improve patient quality of life using pre and post measures. Patient quality of life assessment will be collected at baseline and 6 months for comparison.

Duration of Study	Expected enrollment period is 12 months. Follow-up duration is 6 months from initial replacement procedure with follow-up research visit at week 2 and phone calls at weeks 4 and 6 and month 6 and research visits at months 3, 4 and 6. The study will conclude 6 months from the enrollment of the last subject.

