Study related data, including patient reported outcomes and data collected from the patient electronic medical record will be entered in a password protected database by study personnel, with oversight by Cleveland Clinic Coordinating Center for Clinical Research (C5 Research). C5 Research is an Academic Research Organization (ARO.) An ARO, associated with a university and/or hospital, combines clinical and academic expertise to independently conduct clinical trials and/or to provide services to trial sponsors in the coordination of clinical trials. To protect the patient privacy, all records will be stored by a patient identifier code assigned to the patient at the time of enrollment. The database will be password protected. Only approved research team members associated with this study will have access to these records. The accumulated data will be analyzed and used for reporting purposes. Fees associated with the data capture and analysis will be paid for by the study with no cost to the patient.

Patient characteristics will be summarized as appropriate descriptive statistics. The primary and secondary endpoints will be summarized as frequencies and percentages. Ninety-five % confidence intervals will be also computed. We will also compute the lost to follow-up proportions. All analyses will be conducted with SAS 9.3 (Cary, NC).

Safety and Monitoring

A data Safety Officer (SO) will be assigned to monitor the study data collection, minimally, on a quarterly basis. The Safety Officer will be a CC staff physician, independent of the study team, who will review the accumulating data with regard to recruitment, safety and efficacy. The SO will not be involved in the conduct of this study. The data manager will summarize and report data to the SO at least quarterly, who will review the report and make recommendations to the investigators.

FDA approved, commercially available enteral feeding tube accessories have not been shown to affect mortality. The study stoma site accessory is intended for use with commercially available enteral tubes during a standard of care replacement procedure and is not believed to pose significant risk to its users. EN feeding tube device replacement is performed at CC in both ambulatory and in-hospital settings for patients with varying underlying diseases so, there are expected to be AEs and possible SAEs not related to the study stoma site accessory.

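### The secondary objective is change in quality of life from baseline to month 6, but the analysis text prescribes percentages and names neither a PROMIS 10 score nor an estimate of within-patient change

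*Combined protocol and SAP*

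**What the plan says.** **Objective.** The secondary row of Table 3 (under Primary Outcome Measures) reads "Change in patient quality of life after intervention as self-reported by participants". The Purpose section agrees: "Patients receiving the study accessory will also be asked pre-procedure and post-procedure quality of life questions to identify change in quality of life". The Hypothesis Testing section and the synopsis (Study Hypothesis) both fix the contrast: "Patient quality of life assessment will be collected at baseline and 6 months for comparison".

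**Analysis.** Data Collection and Analysis states: "The primary and secondary endpoints will be summarized as frequencies and percentages". The next sentence adds 95% confidence intervals without saying of what quantity. The looser wording that would admit means or medians is attached to patient characteristics only.

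**Instrument.** PROMIS 10 appears in the acronym list as a ten-question measure and in Table 3 as a validated tool. No section names a score, a scale or a threshold. The Concomitant Therapy section mentions comparing patient-reported outcomes before and after the procedure, again without a method.

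**Timing.** The endpoint cell of Table 3 says "Various participant reported outcomes will be collected at baseline, week 2 and month 6: PROMIS 10". Table 1 marks PROMIS 10 at baseline, early termination and month 6 only, and the week-2 visit list under Follow-Up does not contain it.

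**Status of the hypothesis.** The synopsis (Secondary Endpoints) says "Patient Quality of Life is hypothesized to improve significantly with leak reduction". The Hypothesis Testing section says "This is not a hypothesis driven study" and gives as an aim "feasibility of determining improvement of patient quality of life using pre and post measures".

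**The concern.** Percentages suit procedural success, adverse events and categorical questionnaire items. A multi-item score measured twice in the same patient, with change as the objective, needs a score and a paired estimate. The plan prescribes a type of summary that does not deliver this.

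Any route from PROMIS 10 to a percentage needs a decision that the plan does not record: which score, and how much change counts as improvement. With about 10 patients, that decision would be made with every result in view.

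The handling of early exits is open as well. The synopsis gives month 6 or early termination as the last collection point. Study Duration and Table 3 say that patients with a re-intervention compromising the accessory stay in the endpoint analysis up to that time. Nothing says how their exit score enters a baseline to month-6 contrast.

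The aim at stake is the stated one of showing whether quality-of-life improvement can be determined from before-and-after measures.

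**Working it through.** The plan gives no power, SD, correlation or effect size for quality of life, and the synopsis says no formal sample size calculation was done. There is therefore no figure to reproduce. The check has two parts.

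**1. What the rule yields when followed.**

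| Needed for change in quality of life | Where it might be found | Found? |
|---|---|---|
| Instrument | Table 3 | Yes, PROMIS 10 |
| Time points of the contrast | Hypothesis Testing; synopsis | Yes, baseline and 6 months |
| Score or domain | Acronyms; Table 3; Data Collection and Analysis | No |
| Definition of improvement | Same | No |
| Within-patient estimator | Data Collection and Analysis | No; percentages with 95% CIs |
| Use of early-termination scores in the contrast | Table 1 notes; Study Duration; withdrawal section; Table 3 | Collected and usable; method not stated |

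The literal output is either percentages at each visit or the percentage improved under an unstated rule.

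**2. Illustrative cost of using percent improved.** Assume that within-patient changes are normal, and measure everything in SDs of change. Both are assumptions, and the cut-offs below are not in the plan.

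*Dependence on the cut-off.* Percent improved = Φ(mean change − cut-off).

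| Mean change | Cut-off 0 | Cut-off 0.5 | Cut-off 1 |
|---|---|---|---|
| 0.5 | Φ(0.5) = 69% | Φ(0) = 50% | Φ(−0.5) = 31% |
| 0 | Φ(0) = 50% | Φ(−0.5) = 31% | Φ(−1) = 16% |

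*Efficiency.* The large-sample efficiency of percent improved relative to mean change is φ(d)² / [Φ(d)(1 − Φ(d))], where d is the distance of the cut-off from the mean.

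- d = 0: 0.3989² / 0.25 = 0.637, so 10 pairs carry the information of about 6.4.
- d = 0.5: 0.3521² / (0.6915 × 0.3085) = 0.581.
- d = 1: 0.2420² / (0.8413 × 0.1587) = 0.439, or about 4.4 pairs.

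*Precision of the alternative, for context.* The half-width of a paired 95% t-interval is t(0.975, n − 1)/√n SDs of change: 0.72 for n = 10, 0.84 for n = 8 and 1.05 for n = 6. By comparison, 5 of 10 improved has an exact 95% interval of 19% to 81%.

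The number of pairs is not fixed. Exits after week 2 are not replaced, so it can fall below 10. Enrolment runs until 10 patients have reached week 2, and patients withdrawn before then may also give an early-termination score, so it can exceed 10.

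**The case against.** The strongest reply is that this is a descriptive 10-patient pilot. Quality of life is secondary, no decision rule depends on it, and the instrument and the before-and-after comparison are both stated. A competent analyst would report change anyway, and the raw data are kept. All of that is true, and it limits the weight of the point. It does not remove it: reporting mean change departs from the written rule, and the score and the handling of early exits would be settled with the results known.

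Several stronger readings are tempting, and the documents do not support them.

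- **That the pairing must be lost.** Percentages can be paired, as a shift table or as counts better, same and worse. Nothing orders an unpaired analysis. For a score, such counts still need a rule.
- **That the illustrated losses are those of this plan.** The plan proposes no cut-off. The figures show only what an unstated rule can do under an assumed model, and large-sample efficiency is a rough guide at n = 10.
- **That the synopsis also requires PROMIS 10 at week 2.** It refers to various quality-of-life questionnaires at 2 weeks. The pain and leakage form, which a Table 1 note groups with the quality-of-life questionnaires and which is collected at week 2, could satisfy that. The clear conflict is between Table 3 and the schedule.
- **That a test or a power calculation is missing.** The synopsis expects significant improvement but specifies no test, and the Hypothesis Testing section says none is intended. The conflict is one of wording.

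A further caution concerns the remedy. An analysis confined to patients with a month-6 score would leave out those exited because the accessory failed or was removed, whom Study Duration and Table 3 say are included up to re-intervention.

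**Conclusion.** The point holds as a gap between objective and analysis. The stated rule, applied to PROMIS 10, does not give an estimate of within-patient change, and no score is named. If percent improved were used, it would have at best about 64% of the large-sample efficiency of mean change. That figure rests on normality and on the most favourable cut-off; the documents supply no SD against which to refine it.

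The primary endpoint summaries are unaffected, and the change remains recoverable from stored data. A reader might infer that quality of life cannot be reported at all; that would go too far.

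Separately, Table 3 conflicts with Table 1 and the week-2 visit list on whether PROMIS 10 is collected at week 2. This needs settling before enrolment, because a missed week-2 form cannot be recovered later. The sponsor should correct both; neither calls for more patients or a hypothesis test.

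**What to change.** In Data Collection and Analysis:

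- Keep frequencies and percentages with 95% intervals for procedural success, adverse events and categorical items.
- For PROMIS 10, name the score or scores in advance and list each patient's change. Report mean change (SD) with a paired 95% confidence interval, plus the median, range and number of pairs.
- Give this with equal prominence for (a) patients with a month-6 score and (b) a set that uses the early-termination score where month 6 is missing, stating the day each such score was taken. Note that (a) leaves out patients exited for accessory failure or removal.

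Elsewhere:

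- Reconcile Table 3 with Table 1 and the week-2 visit list on PROMIS 10 at week 2.
- Reword the synopsis secondary endpoint as estimation only, for example: change in quality of life from baseline to month 6 will be estimated with a 95% confidence interval, and no hypothesis will be tested.

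The cost is one paragraph and two small wording edits. No new data are needed if week-2 PROMIS 10 is dropped; keeping it adds one ten-question form per patient.
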